4.4.4. Intraocular Pressure

Intraocular pressure (IOP) will be measured after slit lamp examination has been completed at every study visit. The mean of 3 measurements per eye will be recorded as the IOP.

Measurement should be performed before dilated ophthalmoscopy. The IOP measurement and change from baseline will be summarized using the descriptive statistics by treatment group and visit.

4.4.5. Slit Lamp Examination

A routine slit lamp examination will collect clinical findings from the anterior and posterior segment of both study and fellow eye with pupil dilation and should be conducted after IOP measurement has been completed.

Abnormal slit-lamp biomicroscopy results for the study eye and fellow eye will be summarized by treatment group and visit through week 24 and 52, respectively.

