1.1. Objectives and Endpoints

Objectives	Endpoints
Primary	Primary Efficacy Endpoint The proportion of subjects who have a recurrence of uveitis in the study eye within 24 weeks (6 months) after receiving study treatment
Secondary	Secondary Efficacy Endpoints 
• Proportion of subjects who have a recurrence of uveitis in the study eye within 52 weeks• Mean change from baseline in best corrected visual acuity (BCVA) letter score in the study eye at 24 and 52 weeks• Number of recurrences of uveitis within 24 and 52 weeks• Proportion of subjects with resolution of macular edema as measured by Spectral-domain Optical Coherence Tomography (SD-OCT) imaging at Day 28 and at Months 2, 3, 6, 9, and 12.
Safety	

	
• Systemic Adverse Events (AEs)• Ocular AEs, including IOP elevation• Medications/procedures required to control elevated IOP• Development or worsening of cataract• Cataract-related procedures• Clinically significant ocular changes• Procedure related AEs• Subjective ocular tolerability and discomfort assessments• Vital signs• Clinical laboratory assessments• Use of rescue and concomitant medications
--	--

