4.1. General Considerations

4.1.1. Data Summarization

The Sponsor decided to stop enrollment in early May 2022. Subjects who were randomized to Yutiq 0.05 mg will continue to be monitored on a modified-protocol schedule. The subjects who had been treated with sham injection were discontinued from the study. Consider the fact that the study was terminated early, no statistical hypothesis testing will be performed. All data summaries will be descriptive only, based on observed data.

Tabular data summaries for variables measured on a continuous scale will include descriptive statistics (n, mean, median, standard deviation, minimum, and maximum) by treatment group and visit.

For variables evaluated on a categorical scale, data summaries will include the number and percentage of subjects who provide each possible category, by treatment group and visit when applicable. The 95% confidence interval (CI) of the proportions will be constructed for each treatment group, as appropriate.

All study data will be presented in by-subject listings.

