4.2.2. Analytical Approach for Primary Efficacy Endpoint

The recurrence of uveitis rate will be summarized with the number and percentage of subjects with the recurrence and 95% confidence interval (CI) based on binomial distribution using the Clopper-Pearson (Exact) method.

The vitreous haze score and measurement of BCVA results will be summarized by treatment group at each scheduled visit. Mean change from baseline and proportion of subjects who have an increase of vitreous haze score of ≥ 2 steps, and proportion of subjects who have a deterioration of at least 15 letters BCVA from baseline will be presented at each scheduled visit.

Abnormal vitreous haze for the study eye and fellow eye will be summarized by treatment group and visit.

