4.4.2. Adverse Events

Adverse event data will be coded using the Medical Dictionary for Regulatory Activities (MedDRA). The severity of each AE will be graded by the investigator per CTCAE v5.0 criteria.

Descriptive statistics will be provided for all treatment-emergent adverse events (TEAEs). Both ocular and non-ocular TEAEs are defined as events that start after the study drug administration, and occur before termination of the study, or were present before study drug administration and worsened after dose administration.

Frequency counts and percentage of subjects within each treatment group will be provided by system organ class (SOC) and preferred term (PT) by treatment. Within each level of summarization (SOC, PT), subjects who experience more than one occurrence will only be counted once. Adverse events will also be presented by severity (mild, moderate, severe, life- or sight-threatening), and by relationship to study drug (not related, possibly related, probably related). Listings of deaths, and AEs leading to withdrawal will be presented.

Summaries will be sorted in descending order of frequency in the Yutiq 0.05 mg arm, when applicable. A listing of treatment-emergent AEs, treatment-emergent ocular events, and serious AEs will be provided.

Ocular Adverse Events

The following ocular events will be considered AEs for the purposes of this study:

- Decrease in BCVA of at least ≥ 15 letters or ≥ 3 lines from the previous BCVA measurement
- Moderate or severe (Grade 3 or 4) ocular findings compared to the last ocular examination
- Worsening of >2 steps in anterior chamber cell count or vitreous haze compared to the last ocular examination
- Increase in IOP of >10 mmHg at two visits at least 1 week apart or an increase in IOP to >25 mmHg

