4.4.5.1. Anterior Chamber Cell Grading Scale

Anterior chamber cells will be measured at all study visits and assessment will be made using the following scale (Jabs et al. 2005).

Field size: 1 mm by 1 mm slit beam

0	<1 cells/hpf
0.5+	1-5 cells/hpf
1+	6-15 cells/hpf
2+	16-25 cells/hpf
3+	26-50 cells/hpf
4+	>50 cells/hpf

Anterior Chamber Cell Scoring Convention

The diagram presents the scoring convention that will be used to identify a minimum of “ ≥ 2 step increase” of anterior chamber cells compared to baseline at the Week 24 visit, or any visit time point prior to the Week 24 visit after the Study Day 7 visit.

Anterior Chamber Cell ≥ 2 Step Increase:

Score *	Cell Count*
0	<1 cells/hpf
0.5+	1-5 cells/hpf
1+	6-15 cells/hpf
2+	16-25 cells/hpf
3+	26-50 cells/hpf
4+	>50 cells/hpf

* Jabs et al 2005

The grading scale and measurement of anterior chamber cell results will be summarized by treatment group at each scheduled visit. The proportion of subjects who have an increase of anterior chamber cell of ≥ 2 step increase will be presented.

Abnormal anterior chamber assessment results will be summarized by treatment group and visit.

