4.4.6. Indirect Ophthalmoscopy

Indirect ophthalmoscopy will be performed to assess retinal and choroid appearances and vitreous haze (Nussenblatt et al. 1985). Indirect ophthalmoscopy will be performed for study eye and fellow eye with pupil dilation and should be conducted after IOP measurement has been completed.

Abnormal indirect ophthalmoscopy results for the study eye and fellow eye will be summarized by visit through week 24 and 52 separately.

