6.2.3. Baseline and Disease Characteristics

Optical baseline characteristics include dilated indirect ophthalmoscopy results, baseline BCVA group (\leq 64 vs $>$ 64 letters), BCVA ETDRS letter score, intraocular pressure, ocular tolerability, and anterior, posterior and intermediate slit lamp examinations, and SD-OCT, and will be summarized by treatment group using descriptive statistics with the ITT analysis set.

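### Two safety endpoints worded as change have no named analysis, and outside cells, haze and adverse events the eye-examination tables cannot separate new findings from baseline disease

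*SAP*

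**What the plan says.** SAP 1.1 lists among the safety endpoints "Clinically significant ocular changes", and separately the development or progression of cataract. SAP 1 (Introduction) explains that the endpoint list was cut down after the study was stopped, so these two were kept on purpose. Neither document defines a clinically significant change.

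The analyses of the eye examinations are:

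- Slit lamp (SAP 4.4.5): "Abnormal slit-lamp biomicroscopy results for the study eye and fellow eye will be summarized by treatment group and visit".
- Indirect ophthalmoscopy (SAP 4.4.6): "Abnormal indirect ophthalmoscopy results for the study eye and fellow eye will be summarized by visit through week 24 and 52 separately".
- Default for categorical data (SAP 4.1.1): "data summaries will include the number and percentage of subjects who provide each possible category, by treatment group and visit when applicable".
- Baseline (SAP 6.2.3): "anterior, posterior and intermediate slit lamp examinations, and SD-OCT, and will be summarized by treatment group using descriptive statistics".

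Three parts of the SAP do address worsening:

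- Anterior chamber cells (SAP 4.4.5.1): "The proportion of subjects who have an increase of anterior chamber cell of ≥ 2 step increase will be presented", with the increase measured against baseline.
- Vitreous haze (SAP 4.2.2): mean change from baseline and the "proportion of subjects who have an increase of vitreous haze score of ≥ 2 steps", at each scheduled visit.
- Adverse events (SAP 4.4.2): these include "Moderate or severe (Grade 3 or 4) ocular findings compared to the last ocular examination". Treatment-emergent events are tabulated by system organ class, preferred term and treatment group.

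**The concern.** Both endpoints ask what happened to an eye after injection. The slit-lamp and ophthalmoscopy tables instead report how many subjects are abnormal at a given visit. That count mixes findings present before treatment, findings that have since resolved and findings that are new.

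The mixing matters here because Protocol 4.1 requires a history of recurrent uveitis of more than one year and admits eyes with vitreous haze up to grade 2. Abnormal results at baseline are therefore likely. If inflammation settles in some eyes while a new finding appears in others, a by-visit table can look flat.

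Protocol 1.3 names cataract and raised intraocular pressure as ocular effects of corticosteroids. Pressure is summarised as change from baseline (SAP 4.4.4). The lens has no equivalent summary, although cataract is a listed endpoint.

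**Working it through.** The plan gives no rate or precision for these endpoints, so there is no figure to reproduce. The check has three parts.

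**1. Trace each kind of finding to a summary of change.**

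| Finding | By-visit summary | Summary of worsening |
|---|---|---|
| Anterior chamber cells | SAP 4.4.5.1 | Yes, increase of at least 2 steps from baseline |
| Vitreous haze | SAP 4.2.2 | Yes, mean change and increase of at least 2 steps |
| Findings reported as adverse events | Not applicable | Yes, treatment-emergent tables, SAP 4.4.2 |
| Other slit-lamp findings | SAP 4.4.5 | None |
| Other ophthalmoscopy findings | SAP 4.4.6 | None |

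The gap is the last two rows. I take these to include the lens, cornea, iris, retina and optic nerve. The case report form is not in the documents, so the exact list of structures is an assumption.

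**2. What two by-visit counts can and cannot show.** Take N subjects examined both at baseline and at a visit, with a abnormal at baseline and b abnormal at the visit. Let x be newly abnormal and r resolved. Then b = a − r + x. Since r cannot be negative, x ≥ b − a. Since only subjects normal at baseline can become abnormal, x ≤ N − a, and x cannot exceed b. Hence:

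max(0, b − a) ≤ x ≤ min(b, N − a).

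Set N = 30, the planned arm size in SAP 1.2. The number actually enrolled is not given, and the values of a and b are assumed.

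| a | b | Range of x | Share of 30 | Share of the N − a normal at baseline |
|---|---|---|---|---|
| 6 | 6 | 0 to 6 | 0% to 20% | 0% to 25% (of 24) |
| 12 | 12 | 0 to 12 | 0% to 40% | 0% to 67% (of 18) |
| 12 | 15 | 3 to 15 | 10% to 50% | 17% to 83% (of 18) |
| 18 | 18 | 0 to 12 | 0% to 40% | 0% to 100% (of 12) |
| 24 | 24 | 0 to 6 | 0% to 20% | 0% to 100% (of 6) |

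The range is wide only where findings can resolve. If nothing resolves, r = 0 and x = b − a exactly in a fixed set of eyes. Even then, worsening in an eye already abnormal at baseline is not visible in either count.

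**3. Does the adverse-event route supply the missing summary?** Only in part. SAP 1.1 lists ocular adverse events as an endpoint separate from the two at issue. The examination criterion in SAP 4.4.2 compares with the last examination, not with baseline, so gradual progression over several visits may never meet it. Its threshold is also uncertain: it pairs moderate or severe with Grades 3 or 4, whereas Protocol 8.1.5 calls moderate Grade 2 and severe Grade 3. If the same grading is meant, the two should be reconciled.

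**The case against.** The strongest reply is that the SAP already separates old from new. Protocol 8.1 defines an adverse event to include any new unfavourable sign and any worsening of an existing condition. SAP 4.4.2 counts as treatment-emergent what starts after administration or worsens after it. A new and clinically important lens, retinal or optic-nerve finding should therefore appear in those tables, and SAP 4.1.1 promises by-subject listings in which each eye's sequence can be followed. Cells and haze, for which the documents give grading scales, already have summaries against baseline. Other categorical measures, such as discomfort grade (SAP 4.4.3), are also shown by visit without a shift. The study was stopped, nothing is tested, and the SAP declares a reduced scope.

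Much of this stands. A reader might infer that new or worsened findings are never estimated, or that by-visit abnormal counts are the only display of eye findings. The cell, haze and adverse-event summaries contradict both readings. A reader might also infer that the rate of new findings is left open from 0% to 100%. That follows only from particular assumed counts and from by-visit tables read without the listings. Nor does stopping the sham group distort the Yutiq figures, because the slit-lamp tables are by treatment group. The missing reference to treatment group in SAP 4.4.6 is largely covered by the default in SAP 4.1.1.

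What remains is narrower. Adverse-event reporting depends on the investigator's judgement and on a comparison with the previous visit. Listings are not a summary. Two endpoints that the sponsor chose to keep still have no stated analysis.

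**Conclusion.** The concern holds in a limited form. Two retained safety endpoints have no analysis under their own names. Slit-lamp and ophthalmoscopy findings other than cells, haze and reported adverse events are summarised only as abnormal by visit. Those tables, even alongside the baseline summary, do not give the number of eyes with a new finding.

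The size cannot be stated for this trial, because neither the enrolled number nor the baseline abnormality rate is in the documents. At the planned 30 per arm, equal counts of 12 or 18 at both times leave 0% to 40% of the arm possibly newly abnormal, and counts of 6 or 24 leave 0% to 20%. These figures assume that findings can resolve, that the same subjects are examined at both times, and that the by-visit tables are read alone.

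The consequence is weaker reporting of ocular safety for an intravitreal steroid. No test or decision rule is affected. The change should be made, but the descriptive analysis does not fail without it.

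**What to change.** - In SAP 4.4.5 and 4.4.6 add a shift table for each structure recorded on the case report form, by eye (study and fellow) and treatment group. It should run from baseline, as defined in SAP 4.1.2, to the worst post-baseline result, using normal/abnormal or the grade where one is recorded.
- Add the number and percentage of eyes with a new finding, and with a worsened finding where graded. The denominator is eyes with a baseline and at least one post-baseline examination.
- State that the lens shift serves the cataract endpoint, and say which of these summaries answers the clinically significant change endpoint and what counts as such a change.
- Write the treatment-group split into SAP 4.4.6. Keep the by-visit tables as supportive.
- Show length of follow-up beside the shift tables. Sham subjects were discontinued early while Yutiq subjects continue to Month 12 (Protocol 3.1), so a worst post-baseline result has more chances to occur in the Yutiq group.

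The cost is SAP wording and a few more descriptive tables in a small, terminated study. Protocol Table 5-1 already schedules these examinations at every visit. Worsening can be shown only for structures with a recorded grade; for the rest the table shows new findings alone.

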4.4.5.1. Anterior Chamber Cell Grading Scale

Anterior chamber cells will be measured at all study visits and assessment will be made using the following scale (Jabs et al. 2005).

Field size: 1 mm by 1 mm slit beam

0	<1 cells/hpf
0.5+	1-5 cells/hpf
1+	6-15 cells/hpf
2+	16-25 cells/hpf
3+	26-50 cells/hpf
4+	>50 cells/hpf

Anterior Chamber Cell Scoring Convention

The diagram presents the scoring convention that will be used to identify a minimum of “ ≥ 2 step increase” of anterior chamber cells compared to baseline at the Week 24 visit, or any visit time point prior to the Week 24 visit after the Study Day 7 visit.

Anterior Chamber Cell ≥ 2 Step Increase:

Score *	Cell Count*
0	<1 cells/hpf
0.5+	1-5 cells/hpf
1+	6-15 cells/hpf
2+	16-25 cells/hpf
3+	26-50 cells/hpf
4+	>50 cells/hpf

* Jabs et al 2005

The grading scale and measurement of anterior chamber cell results will be summarized by treatment group at each scheduled visit. The proportion of subjects who have an increase of anterior chamber cell of ≥ 2 step increase will be presented.

Abnormal anterior chamber assessment results will be summarized by treatment group and visit.

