Eligibility determination, informed consent, demographics, medical and ophthalmic history (including a detailed history of the management of their uveitis over the previous 52 weeks), vital signs, clinical laboratory testing, ophthalmic examinations (includes BCVA, IOP, dilated ophthalmoscopy, and anterior, posterior and intermediate slit lamp examination), subjective ocular tolerability and discomfort assessment, concomitant medications, and pregnancy testing as appropriate.

Treatment Day (Day 1):

Eligibility confirmation including meeting the entry criteria for anterior chamber cells, vitreous haze, IOP, and visual acuity on Study Day 1, and then randomization to either intravitreal Yutiq 0.05 mg or sham injection. Following determination of study eye, subjects will receive either Yutiq 0.05 mg or the sham injection. Assessments on that day will include vital signs, ophthalmic examinations, spectral-domain – optical coherence tomography (SD-OCT), subjective ocular tolerability and discomfort assessment, pregnancy test if appropriate, concomitant medications, and adverse events (AEs).

Follow-up Visits:

Following injection on Study Day 1, subjects who were treated with Yutiq 0.05 mg will return for study visits on Days 7, 28, and at Months 2, 3, 6, and 12. Evaluations on these days will include: review of concomitant medications, vital signs, ophthalmic examinations, IOP, SD-OCT, subjective ocular tolerability and discomfort assessment, and AEs. All subjects treated with Yutiq 0.05 mg in the study will be followed for 52 weeks. In early May 2022, those subjects who had been treated with sham injection were discontinued from the study. Sham-treated subjects subsequently had their End of Study (EOS) evaluation.

Masking: Study subjects will receive either Yutiq 0.05 mg or a sham injection. Subjects and study staff conducting clinical study assessments, except for the clinician performing the injection procedure, will be masked to randomized treatment assignment.

Concomitant Medications:

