4.1.3. Analysis Visit Windows

There will not be visit date re-mapping for the data analyses. All analyses will be descriptive. Descriptive summary tables will be based on nominal visits.

- Efficacy endpoints labelled as Week 24 endpoint will use the assessments from Month 6 visit.
- Efficacy endpoints labelled as Week 52 endpoints will use the assessments of Month 12 visit.

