4.2. Primary Efficacy Endpoint Analysis

4.2.1. Definition of Endpoint

The primary efficacy endpoint is the proportion of subjects who have a recurrence of uveitis in the study eye within 24 weeks (6 months) after receiving study treatment. Recurrence is defined as:

- An increase in the vitreous haze of ≥ 2 steps compared to baseline at the Week 24 visit, or any visit time point prior to the Week 24 visit after the Study Day 7 visit

Or

- A deterioration in visual acuity of at least 15 letters BCVA compared to baseline at the Week 24 visit, or any visit time point prior to the Week 24 visit after the Study Day 7 visit.

Any criterion used to define recurrence must be attributable only to noninfectious uveitis. To prevent post-procedural inflammatory reactions from being reported as uveitis recurrences, assessments for recurrence of uveitis begin after the Study Day 7 visit.

The study protocol stated to impute subjects who don't complete Week 24 eye examinations and subjects who take prohibited medications as having a recurrence. Consider the fact that the study was terminated early, no imputation will be implemented. Summary of the primary efficacy endpoint will be based only on the observed data from the subjects who reached Week 24.

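### The safety proportion for a ≥2-step anterior chamber cell increase (SAP 4.4.5.1) carries the efficacy recurrence window, so as written it omits Day 7 and Month 12

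*SAP*

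**What the plan says.** SAP 4.4.5.1 (Anterior Chamber Cell Grading Scale) stands under 4.4 Safety Analyses. It says that cells are graded at every study visit. It then introduces the scoring convention for a ≥2-step increase, measured against "baseline at the Week 24 visit, or any visit time point prior to the Week 24 visit after the Study Day 7 visit". The planned output follows: "The proportion of subjects who have an increase of anterior chamber cell of ≥ 2 step increase will be presented". That sentence states no window of its own and does not ask for results by visit.

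The vitreous haze and visual acuity criteria of the primary efficacy endpoint in SAP 4.2.1 use the same window: "compared to baseline at the Week 24 visit, or any visit time point prior to the Week 24 visit after the Study Day 7 visit". SAP 4.2.1 also gives the reason for the late start: "To prevent post-procedural inflammatory reactions from being reported as uveitis recurrences, assessments for recurrence of uveitis begin after the Study Day 7 visit".

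Two other safety provisions bear on the point. SAP 4.4.2 names findings that count as ocular adverse events, among them "Worsening of >2 steps in anterior chamber cell count or vitreous haze compared to the last ocular examination". SAP 1.1 lists "Procedure related AEs" as a safety endpoint.

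For the visit schedule, the Protocol Synopsis (Follow-up Visits) says that treated subjects "will return for study visits on Days 7, 28, and at Months 2, 3, 6, and 12".

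**The concern.** The start of the window serves a purpose in efficacy. Early inflammation caused by the injection should not be counted as a return of the disease. In a safety summary that purpose disappears, because early inflammation after an intravitreal insert is something the summary ought to show. Day 7 is the only scheduled visit between the injection and the Day 28 visit, so it is the natural place to look.

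The end of the window is also out of line with the rest of the safety plan. SAP 4.4.1 describes 52 weeks of follow-up after treatment, and the parent section 4.4.5 reports abnormal slit-lamp findings through Weeks 24 and 52. A Week 24 limit on this one proportion has no stated reason.

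At stake is one reported safety figure. It could be smaller than the collected data would make it, and a reader of the table would have no sign that two visits had been left out.

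**Working it through.** The documents give no figure on this point, so there is none to reproduce. The check has three parts.

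**1. Visits inside and outside the window.** The visits are those of the treated arm in the Protocol Synopsis and Table 5-1. The Week 24 limit is placed at Month 6 because SAP 4.1.3 says: "Efficacy endpoints labelled as Week 24 endpoint will use the assessments from Month 6 visit". That mapping is stated for efficacy endpoints; I assume it holds here too.

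| Scheduled visit | After Day 7 visit? | No later than Week 24? | Counted? |
|---|---|---|---|
| Day 7 | no | yes | no |
| Day 28 | yes | yes | yes |
| Month 2 | yes | yes | yes |
| Month 3 | yes | yes | yes |
| Month 6 | yes | yes | yes |
| Month 12 | yes | no | no |

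Counted: 4 of 6. Left out: 2 of 6 = 33%. Any unscheduled or early termination examination after Month 6 is also left out.

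**2. Does the ocular adverse event trigger pick up what the proportion drops?** Inclusion criterion 4 requires fewer than 10 cells per field in the study eye, so the baseline grade is 0, 0.5+ or 1+. I count one scale category as one step, because the step diagram is not reproduced in the text available. On the scale 0, 0.5+, 1+, 2+, 3+, 4+:

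- Rises of ≥2 steps: from 0, four (to 1+, 2+, 3+, 4+); from 0.5+, three (to 2+, 3+, 4+); from 1+, two (to 3+, 4+). Total 4 + 3 + 2 = 9.
- Rises of >2 steps: 3 + 2 + 1 = 6.
- Difference: 9 − 6 = 3, namely 0 to 1+, 0.5+ to 2+, and 1+ to 3+.

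These three exact two-step rises, seen only at Day 7 or Month 12, enter neither the proportion nor the >2-step trigger. Two qualifications apply. First, the trigger compares with the last examination, not with baseline. At Day 7 the last scheduled examination is Day 1, so the two references agree. At Month 12 it is normally Month 6, so an eye that had fallen below its baseline grade could meet the trigger with a rise of only two steps from baseline. From baseline 0 this cannot happen. Second, a rise to 3+ might meet the separate trigger for Grade 3 or 4 ocular findings.

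**3. Illustration of scale.** The documents give neither the number enrolled nor a rate of cell increases, so a per-visit chance p must be assumed. With p constant and visits independent, the chance that a subject is flagged at least once is 1 − (1 − p)^k over k visits.

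| p (assumed) | k = 4, as written | k = 6, all visits |
|---|---|---|
| 2% | 1 − 0.98^4 = 7.8% | 1 − 0.98^6 = 11.4% |
| 5% | 1 − 0.95^4 = 18.5% | 1 − 0.95^6 = 26.5% |
| 10% | 1 − 0.90^4 = 34.4% | 1 − 0.90^6 = 46.9% |

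Neither assumption is likely to hold exactly. Correlation between visits would usually narrow the gap, and a higher chance at Day 7 than at other visits would widen it. The table shows only that the omission can move the figure noticeably.

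**The case against.** The strongest reply is that little is really missing. SAP 4.4.5.1 itself summarises cell grades at each scheduled visit and abnormal anterior chamber results by visit. SAP 4.4.5 does the same for abnormal slit-lamp findings through Week 52. SAP 4.1.1 promises by-subject listings of all data, and in a stopped, purely descriptive study a reader can follow each eye through them. All of this stands. A reader might infer that first-week or late inflammation is hidden from safety reporting; the documents do not support that. What the by-visit summaries do not give is the count of subjects whose own grade rose by two or more steps.

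A reader might also infer that the adverse event route cannot recover these cases. That goes too far. The list in SAP 4.4.2 names findings that must count as adverse events, and it does not narrow the general definition in Protocol 8.1, which includes complications of protocol procedures. An investigator may report a two-step rise. Only automatic capture by the >2-step rule is lost.

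Nor does the window bias the procedure-related adverse event endpoint. That endpoint rests on reported events and the investigator's judgement of their relationship to the procedure (Protocol 8.1.5 and 8.2), with no Day 7 exclusion. The cell-grade proportion does not feed it.

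Two further points have weight. The window stands in the sentence on the scoring convention and is not repeated in the output sentence, so a programmer could produce the proportion without it. That makes the effect uncertain, but it also shows that the text needs to say which reading is meant. And the flag has an efficacy history: Protocol Appendix 2 ties the cell convention to the primary efficacy endpoint, and Protocol 10.2 has an iridocyclitis recurrence endpoint that the SAP's reduced list omits. This suggests carried-over wording rather than a choice made to favour the insert. It does not explain the Week 24 limit, since the protocol endpoint also ran to 52 weeks.

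Finally, sham subjects were discontinued around early May 2022, so restoring Month 12 may add little comparison between arms. It would still describe the treated arm.

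**Conclusion.** The point holds for one descriptive safety proportion. If the convention sentence in SAP 4.4.5.1 governs the output, the only planned summary of within-subject ≥2-step change in anterior chamber cells covers 4 of 6 scheduled post-injection visits and leaves out Day 7 and Month 12. The reason given for leaving out Day 7 applies to recurrence, and none is given for stopping at Week 24. The contrast with SAP 4.2.2, which presents the ≥2-step vitreous haze proportion at each scheduled visit, shows that a by-visit layout is already in use in this plan.

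The consequence is limited: a possibly understated figure in one table, with the underlying data visible elsewhere. The size in subjects cannot be stated from the documents. The conclusion rests on three assumptions: that the window applies to the output sentence, that Week 24 means the Month 6 visit here as it does for efficacy, and, for the step counts, that one scale category is one step.

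**What to change.** In SAP 4.4.5.1, remove the after-Day-7 start and the Week 24 limit for the safety summary. State that the proportion with a ≥2-step increase from baseline will be presented by treatment group:

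- at each scheduled visit, including Day 7 and Month 12, as SAP 4.2.2 already does for vitreous haze; and
- at any post-injection examination through Month 12 or end of study/early termination.

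Keep the after-Day-7 rule in the recurrence definition of SAP 4.2.1, where its reason applies. Also state in words that one step is one category of the printed scale, if that is what the diagram shows.

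The cost is a change of wording and a few extra rows in one table. No new data are needed, since cells are graded at all visits. The treated-arm figure may come out less favourable than under the present wording.
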